8.7.1.4 Analysis of Safety Variables

Adverse events (AEs) will be tabulated by overall, system organ class (SOC), and Preferred Term using the MedDRA v.16.0 coding system. Incidence and percentage of adverse events, by dose and overall. Additional tables, with AEs subset by severity and by relationship to drug as assessed by the investigator will be presented. Subset listings will be produced for adverse events that cause withdrawal and for SAEs.

Laboratory data, vital signs and ECGs will be summarized using descriptive statistics. Important changes in laboratory, ECG values and vital signs will be flagged in data listings. Listings of most abnormal changes will be provided.

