2. STATISTICAL METHODS

2.1 GENERAL CONSIDERATIONS

In general, continuous variables will be summarized by number of subjects, mean, standard deviation (SD), median, minimum, and maximum values. Categorical variables will be summarized by counts and percentage of subjects in each category. If data is sparse, no summary table will be presented. Summary tables will present data by treatment received during the this study, i.e. Ganaxolone. Source data for the summary tables and statistical analyses will be presented as subject data listings, which include data collected on the electronic case report forms (eCRFs) as well as any derived variables for all enrolled subjects.

Baseline seizure activity will be determined by 8 weeks of retrospective recording in subject daily seizure calendars in Study 1042-0603.

Baselines for safety assessments are defined as the last non-missing value of the assessment before the first dose of treatment in Study 1042-0603.

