5. STUDY DRUG AND EXPOSURE

5.1 EXTENT OF EXPOSURE

Exposure to study medication will be summarized as a continuous variable, via the number of days of drug taken. Ganaxolone will be administered BID following the morning and evening meals. A missed dose of study medication may be taken later up to 8 hours before the next scheduled dose; otherwise, the missed dose should not be given. Treatment exposure and treatment compliance will be summarized using the Safety population.

- Treatment Exposure = the number of days of drug taken = drug stop date – start date + 1
- Treatment Compliance % = $[(\text{drug stop date} - \text{start date}) + 1 - \text{number of days drug not taken}] / [(\text{drug stop date} - \text{start date}) + 1] \times 100\%$.

A subject data listing will be provided for study drug dispense and return.

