7. SAFETY ANALYSIS

All safety analyses will be performed by treatment, i.e. Ganaxolone, in the Safety Population. Safety assessments include:

- AE
- Clinical laboratory tests
- Vital signs including temperature, blood pressure, pulse rate, and weight
- 12-lead ECG
- Physical and neurological examinations
- Columbia-Suicide Severity Rating Scale (C-SSRS)

Baseline is defined as the last non-missing value obtained before the first treatment in the preceding Study 1042-0603.

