7.1 ADVERSE EVENTS

Adverse events (AEs) will be coded by System Organ Class (SOC) and Preferred Term (PT) using the Medical Dictionary for Regulatory Activities (MedDRA®, version 16.0/AECODE). The verbatim term will be included in the AE listings.

A treatment-emergent adverse event (TEAE) is defined as an AE that occur or worsen on or after the first dose of study drug in Study 1042-0604 and before the end of the study (including the safety follow-up period). Only TEAEs will be included in summary tables. All AEs, treatment emergent or otherwise, will be presented in subject data listings.

The TEAEs will be summarized as the number (percentage) of subjects with TEAEs within SOC and PT. Subjects who report the same PT on multiple occasions will be counted once for the PT: under the highest severity (severe > moderate > mild) when summarized by severity and under the closest relationship (related > probably related > possibly related > unlikely related > Not related) to study drug when summarized by relationship. If a subject reports multiple PT for a SOC, the subject will be counted only once for that SOC. Treatment related AEs are defined as those events recorded on the CRF as 'Related', 'Probably Related' or 'Possibly Related', others will not be related AEs.

TEAEs will be summarized as below.

- An overview table, including number of subjects with
 - TEAEs
 - serious AEs (SAEs)
 - study drug related TEAEs
 - TEAEs by severity

- TEAEs leading to study discontinuation
- TEAEs leading to death
- TEAE by SOC and PT
- TEAE by SOC, PT, and Severity
- TEAE by PT
- TEAEs by SOC, PT, and Relationship to Study Drug

All AE tables will be sorted by SOC and PT in decreasing frequency of the number and percentage of subjects.

Missing date will be imputed followed table describes how missing date information will be handled:

Partial Missing Start or Stop Date	Imputed Start Date	Imputed Stop Date
Missing month and day, and the year is present	January 1 of that year or first dose date if the year is the same as the year of first dose date	December 31 of that year
Missing day, but year and month are present	First day of that month or first dose date if the year and month are the same as the year and month of first dose date	Last day of that month
Missing month, but year and day are present	Missing month imputed as January	Missing month imputed as December

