9. SUMMARY OF MAJOR CHANGES IN THE PLANNED ANALYSES

Below changes from protocol have been made in the SAP.

Safety Endpoints:

Due to early termination of the study and low patient numbers 12-lead ECG and Neurological Examination results will only be reported in listings. C-SSRS data were collected in eCRF and will be reported as one of the safety endpoints.

Efficacy Endpoints:

Due to early termination of the study and low patient numbers seizure free intervals and seizure free days will not be derived and the Clinician's Global Impression of Improvement, and the Patient/Caregiver Global Impression of Improvement results will only be reported in listings

To avoid confusion, protocol defined primary and secondary efficacy endpoints are re-named as main and other efficacy endpoints, respectively, to clarify that the primary objective of the study is to assess the safety and tolerability of adjunctive ganaxolone during two-year open-label treatment in adult subjects with drug-resistant partial-onset seizures.

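### TEAEs are planned only as pooled n (%): the protocol's by-dose incidence is dropped without being declared, and a patient-year rate would be a cheap addition for a two-year safety objective cut short

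*SAP*

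**What the plan says.** **Protocol.** Section 8.7.1.4 plans "Incidence and percentage of adverse events, by dose and overall", with further tables by severity and by relationship to drug. It does not define dose for this purpose (at entry, at onset, modal or last).

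**SAP.** The general rule in 2.1 is "Summary tables will present data by treatment received during the this study, i.e. Ganaxolone". Section 7 repeats it for safety: "All safety analyses will be performed by treatment, i.e. Ganaxolone, in the Safety Population". Section 7.1 gives the statistic: "The TEAEs will be summarized as the number (percentage) of subjects with TEAEs within SOC and PT". The tables it lists are an overview, SOC/PT, severity, PT alone, and relationship. None is by dose, and none has a time denominator.

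Three other passages bear on the point:

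- SAP 2.1 has a general sparse-data rule: "If data is sparse, no summary table will be presented".
- SAP 5.1 derives days of exposure per subject: "Treatment exposure and treatment compliance will be summarized using the Safety population".
- SAP 9 opens with "Below changes from protocol have been made in the SAP". It gives "Due to early termination of the study and low patient numbers" as the reason for moving ECG, neurological and global-impression results to listings and for not deriving the seizure-free measures. It also records the added C-SSRS reporting and the renaming of the efficacy endpoints. The by-dose AE table is not on the list.

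**The concern.** Safety and tolerability over two years is the primary objective, so the TEAE tables carry the main result. Two separate things are at stake.

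The first is traceability. The protocol planned a view of AEs by dose, and its Introduction describes most AEs in the programme as dose-related. The SAP leaves that view out and does not say so, although it takes care to declare smaller changes.

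The second is interpretation. The study stopped early. The withdrawal criteria in protocol 8.3.4.1, which include AEs and loss of response, make unequal follow-up likely. A percentage of subjects with an event then mixes how often events occur with how long people were watched. Nothing in the TEAE tables tells the reader which.

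**Working it through.** The plan states no AE rate, achieved sample size or achieved exposure, so there is no figure of its own to reproduce. The first and last steps compare text. The arithmetic between them is illustration under stated assumptions.

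**1. Text side by side**

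| Item | Protocol 8.7.1.4 | SAP 2.1, 7, 7.1 | Declared in SAP 9? |
|---|---|---|---|
| AE incidence overall | planned | planned | not a change |
| AE by severity, by relationship | planned | planned | not a change |
| AE incidence by dose | planned | absent | no |
| AE rate per patient-year | not planned | absent | not a change |

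Only the third row is a departure from the protocol.

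**2. How far n (%) depends on follow-up**

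Assume a constant first-event rate λ and equal follow-up of w weeks, so T = w × 7/365.25 years. The expected proportion with an event is 1 − exp(−λT).

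| λ per patient-year (assumed) | 17 wk | 34 wk | 52 wk | 104 wk |
|---|---|---|---|---|
| 0.10 | 3.2% | 6.3% | 9.5% | 18.1% |
| 0.25 | 7.8% | 15.0% | 22.1% | 39.2% |
| 1.00 | 27.8% | 47.9% | 63.1% | 86.4% |

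At λ = 0.25 the same rate gives percentages about five-fold apart (39.2/7.8). Put another way, for a true two-year risk of 20% with constant hazard, the crude figure is 1 − 0.8^(w/104): 5.4% at 26 weeks, 10.6% at 52, 15.4% at 78 and 20.0% at 104. There is no understatement if everyone reaches week 104, or if all events fall before follow-up ends.

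**3. Precision of a rate at low numbers**

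The exact Poisson 95% interval for x first events over PY patient-years at risk runs from χ²(0.025; 2x)/(2PY) to χ²(0.975; 2x+2)/(2PY). Assume λ = 0.25 and 34 weeks each (T = 0.652 years), so that PY = N(1 − exp(−λT))/λ.

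- N = 20: PY = 12.0, x = 3, rate 24.9 per 100 patient-years (5.1 to 72.9).
- N = 100: PY = 60.1, x = 15, rate 24.9 (14.0 to 41.1).

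(Rates use unrounded PY.)

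**4. How fine a dose split could be**

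The maintenance range of 900 to 1800 mg/d in 225 mg/d steps (protocol 8.4.4) gives (1800 − 900)/225 + 1 = 5 levels. For a level with no events among n subjects, the upper limit of the exact two-sided 95% interval is 1 − 0.025^(1/n): 60.2% for n = 4, 36.9% for n = 8 and 20.6% for n = 16. These n are assumed. Only a few categories would be workable.

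**5. Are the data there?**

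Protocol 9.5.2 requires AE start and end dates, and SAP 5.1 uses drug start and stop dates. The TEAE window in SAP 7.1 includes safety follow-up, so time at risk also needs the end-of-study date. If two weeks of follow-up lay wholly beyond the drug stop date, that would be 2/19 = 10.5% of total time for a 17-week subject and 2/106 = 1.9% for a 104-week subject. These are upper bounds, because taper days on drug already count as exposure. Neither document shows that dated dose changes were captured.

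**The case against.** The strongest reply on dose is that the loss is small and partly foreseen. The protocol phrase is undefined, and dose may change every three days and is adjusted for tolerability, so any split is confounded. SAP 2.1 withholds tables when data are sparse, SAP 9 records low numbers, and its heading speaks only of major changes. This limits the value of the table but does not explain the silence. The sparse-data rule is conditional and is never tied to this analysis, while Section 9 gives reasons for other dropped items and lists even the renaming of endpoints. SAP 6.3 plans no subgroup analysis, but it sits in the efficacy section.

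On rates, the reply is that n (%) is a coherent description for a single-arm study with no comparison, that exposure is summarised in the same population, and that early termination is stated openly. All of this stands, which is why the rate is an improvement and not a correction.

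A reader might infer that the absence of a rate hides time to first event. The documents do not support this: SAP 2.1 and 7.1 put all AEs in subject listings, and AE dates are collected, so it can be recovered subject by subject apart from partial dates. A reader might also fault the error from dividing event counts by number of subjects times mean exposure, but the SAP never proposes that calculation.

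**Conclusion.** The undeclared loss of by-dose AE incidence is established from the text alone. It is a modest fault: the table would be descriptive, confounded and probably sparse, but it was a planned part of the primary-objective analysis.

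The case for a patient-year rate rests on the stated early termination and on follow-up that is likely, not shown, to be unequal. It is tempting to say that the planned percentages understate two-year risk. The documents do not support that as a charge against the plan. The SAP never presents them as two-year risks, and they are valid as observed proportions. The size of any understatement under that reading cannot be computed without subject, event and exposure totals. The figures above show only that the dependence on follow-up can be large under a constant hazard.

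**What to change.** 1. **Rates.** In the SAP 7.1 overview rows (any TEAE, SAE, related TEAE, TEAE leading to discontinuation), and optionally the SOC/PT table, add subjects with a first event per 100 patient-years at risk, with exact Poisson 95% CI. Time at risk runs from the first 1042-0604 dose to the first event or the end of the TEAE window including safety follow-up, so it uses the end-of-study date and not only the drug stop date. Footnote n (%) as observed over actual exposure, in subjects selected for response and tolerability in 1042-0603.
2. **Dose.** Add a descriptive TEAE table by a pre-stated category that the collected data support, for example dose at rollover. Use modal dose or dose at onset only if dated dose history was captured, since both need it. Note the confounding by dose adjustment for tolerability. If the table is too sparse under SAP 2.1, declare the omission and the reason in Section 9.

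**Cost.** SAP text and programming for the rates; a definition and one table, or one sentence, for dose.

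**Downsides.** Intervals will be wide at low numbers. SAP 7.1 imputes partial start dates to the earliest date, or to the first-dose date, which shortens time at risk: by up to 30 days if the day is missing and up to about a year if month and day are missing. The number imputed should be reported. Converting a rate to a two-year risk would need constant hazard and non-informative censoring, which is doubtful when withdrawal is tied to AEs and loss of response.

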8.6 Data Quality Assurance

Steps to be taken to assure the accuracy and reliability of safety data include the selection of qualified Investigators and appropriate study centers, review of protocol procedures with the Investigator and associated personnel prior to the study, and periodic monitoring by a Sponsor representative. Case report forms will be reviewed for accuracy and completeness by a Sponsor representative during on-site monitoring visits and after their return to the Sponsor, and any discrepancies will be resolved with the Investigator or designees, as appropriate. The data will be entered into the clinical trial database and verified for accuracy.

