9.5.2 Evaluating and Recording of Adverse Events

At each visit all adverse events that are observed, elicited by the Investigator, or reported by the subject, will be recorded in the appropriate section of the AE CRF and evaluated by the Investigator.

Minimum information required for each AE includes type of event, duration (start and end dates), severity, seriousness, causality to study drug, action taken, and outcome.

Severity of AEs will be graded by the Investigator using the following criteria as guidelines:

1. Mild: Nuisance, barely noticeable.
2. Moderate: Uncomfortable, troublesome symptoms not significantly interfering with daily activities or sleep.
3. Severe: Symptoms significantly interfere with daily activities or sleep.

The relationship of the AE to the study drug should be specified by the Investigator, using the following definitions:

1. Not Related: Concomitant illness, accident or event with no reasonable association with study drug.
2. Unlikely Related: The event has little or no temporal sequence from administration of the study drug, and/or a more likely alternative etiology exists.
3. Possibly Related: The event follows a reasonable temporal sequence from administration of study drug **but which could also be explained** by concurrent disease or other factors or medications.
4. Probably Related: The event follows a reasonable temporal sequence from administration of study drug, **but is unlikely to be attributed** to concurrent disease or other factors or medications. A clinically reasonable response may be observed if the study drug is withdrawn or dose reduced.
5. Definitely Related: the event follows a reasonable temporal sequence from administration of study drug and is definitive pharmacologically; cannot be attributed to concurrent disease or other factors or medications. A clinically reasonable response

should be observed if the study drug is withdrawn or dose reduced.

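### SAP 7.1 defines treatment-related AEs by CRF labels that omit the protocol's top causality grade, 'Definitely Related', and no mapping between the two scales is stated

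*SAP*

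**What the plan says.** Protocol 9.5.2 lists five grades of relationship to study drug: Not, Unlikely, Possibly, Probably and Definitely Related. The top one is defined as follows: "Definitely Related: the event follows a reasonable temporal sequence from administration of study drug and is definitive pharmacologically". The same section makes causality part of the minimum information for every AE ("severity, seriousness, causality to study drug, action taken, and outcome"). Protocol 8.7.1.4 promises tables of "AEs subset by severity and by relationship to drug as assessed by the investigator".

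SAP 7.1 uses the relationship in two ways.

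- **A yes/no flag.** "Treatment related AEs are defined as those events recorded on the CRF as" one of three labels, with a catch-all for the rest: "Related', 'Probably Related' or 'Possibly Related', others will not be related AEs". The flag feeds the overview row for drug-related TEAEs.
- **A hierarchy.** A subject with repeated reports of a preferred term (PT) is counted once, at the closest relationship, in this order: "related > probably related > possibly related > unlikely related > Not related". The hierarchy feeds the table by SOC, PT and relationship.

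The word 'definitely' does not occur in the SAP as a causality grade. The changes listed in SAP 9 do not mention the causality scale.

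**The concern.** The flag depends on the recorded label, and every label outside the three named is sent to the not-related side. The protocol's strongest grade is not among the three. Applied to the protocol's own scale, the stated rule therefore puts 'Definitely Related' together with 'Unlikely' and 'Not Related'. An error of this kind could only lower the number of related events.

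Safety and tolerability is the primary objective, and the affected outputs are its relationship summaries.

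Elsewhere the SAP does record its renamings. Section 2.2.1 notes the protocol's name for the safety population, and section 9 explains why the efficacy endpoints were relabelled. The causality label has no such note.

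**Working it through.** There is no figure in the plan to reproduce. The check is a comparison of labels.

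**Step 1. The two scales side by side, strongest first.**

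| Rank | Protocol 9.5.2 | SAP 7.1 hierarchy | Same name? | Named in the SAP as related? |
|---|---|---|---|---|
| 1 | Definitely Related | related | no | 'Related' only |
| 2 | Probably Related | probably related | yes | yes |
| 3 | Possibly Related | possibly related | yes | yes |
| 4 | Unlikely Related | unlikely related | yes | no |
| 5 | Not Related | Not related | yes | no |

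Four of five names match. One is unmatched on each side, and both unmatched names stand at the top rank.

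**Step 2. The flag under each possible CRF wording.**

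- *CRF prints 'Related'.* All 3 defining labels exist as stored values (3 of 3). No event is lost, and only the wording of protocol and SAP differs.
- *CRF prints 'Definitely Related' and the rule is read literally.* Related = {Probably, Possibly} = 2 of 5 grades. Others = {Definitely, Unlikely, Not} = 3 of 5. Of the 3 defining labels, 3 − 2 = 1 matches no stored value.

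**Step 3. What happens to a subject in the second case.**

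- Overview row: a subject drops out only with at least one TEAE graded Definitely and none graded Probably or Possibly.
- Relationship table, all reports of a PT graded Definitely: the subject has no rank for that PT. The PT is counted in the SOC/PT table but at no level of the relationship table, so the gap can be seen.
- Relationship table, one PT graded once Definitely and once Possibly: the subject appears under Possibly. There is no gap, but the closest relationship is understated.

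**Step 4. Search for a mapping.** None appears in the text available. Protocol text between 9.5.2 and 9.5.3.3, on AE reporting, was removed before review and could not be checked. The Synopsis and exclusion criterion 2 also use 'probably or definitely'. They concern events in Study 1042-0603, so they show the protocol's vocabulary but not this study's CRF code list.

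**Step 5. Size.** The documents give neither AE counts nor the AE CRF, so no estimate of affected events or subjects is possible.

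**The case against.** The best defence is that the SAP may simply be quoting the CRF. It puts the three labels in quotation marks and ties them to what the CRF records. SAP 9 describes a study that had ended early with data already collected in the eCRF, so its authors could have seen the form. The harmful case then requires the SAP to misquote the form it names. Both scales also have five ordered levels and the lower four match by name, so only one alignment makes sense and a programmer would probably use it. This argument stands, and it is why the point is minor. It does not remove the point, because the equivalence is inferred and a pre-specified definition should state it.

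The practical consequence is also limited. The study is single-arm and descriptive, with low patient numbers. "All AEs, treatment emergent or otherwise, will be presented in subject data listings", and SAEs, AEs leading to discontinuation and deaths have their own listings. A misclassified event could therefore be found by reading the listings, though the summary row would still be wrong.

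A reader might also infer that the catch-all classes events with a blank causality grade as not related. The documents do not support that as a stated rule. The SAP never mentions missing causality, and 'others' can simply mean the two remaining grades, Unlikely and Not Related. SAP 2.5 offers a competing rule of no imputation and analysis of available data. Blanks should in any case be few, since causality is required for each AE and "Case report forms will be reviewed for accuracy and completeness by a Sponsor representative during on-site monitoring visits".

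**Conclusion.** The mismatch is certain from the text: the protocol's top grade is absent from the SAP's definition of treatment-related and from its hierarchy, and the text available states no mapping. The consequence is conditional. It is zero if the CRF prints 'Related', or if the programmer maps the top grades to each other. It is a downward error in the related counts only if the CRF prints 'Definitely Related' and the rule is applied literally.

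A reader might conclude that the SAP does exclude the strongest grade from the related events. The documents do not show this. They do not include the CRF, and the SAP's own ranking points the other way.

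Minor. The conclusion assumes that the protocol text not available for review contains no mapping.

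**What to change.** 1. Check the AE CRF code list for the wording of the top grade.
2. In SAP 7.1, define treatment-related as Definitely, Probably or Possibly Related. If the CRF prints 'Related', keep that label and state that it is equivalent to the protocol's 'Definitely Related'.
3. Use the same labels in the hierarchy.
4. Optional: query missing causality grades and show any that remain in a separate 'missing' row, so that 'others' is not read as covering them. Such a row needs no imputation and so agrees with SAP 2.5.

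The cost is one or two sentences in the SAP and a look at one code list. Steps 1 to 3 need no new data. The number of related events may rise slightly if the literal rule would otherwise have been programmed.

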8.3.4 Removal of Subjects from Therapy or Assessments

8.3.4.1 Criteria for withdrawal

All subjects reserve the right to withdraw from the clinical study at any time, as stated in the informed consent form (ICF). The Investigator may discontinue subjects from the clinical study for any of the following reasons:

1. QTc interval >500 msec or uncorrected QT interval >600 msec; for subjects with bundle branch block, QTc >530 msec based on average QTc value of triplicate ECGs. A subject with an increase in QTc of >60 msec from Visit 1 must also be withdrawn.
 - a. If an ECG indicates a QTc interval outside of these limits, then 2 additional ECGs should be collected and the average QTc value of these 3 ECGs will be used. If the average values of the triplicate ECGs exceed the stated limits, the subject must be withdrawn.
2. Subject is found to have entered the clinical investigation in violation of the protocol;
3. Subject requires the use of an unacceptable or contraindicated concomitant medication. Should a prohibited CYP 3A 4, 5, 7 inhibitor or inducer be required for short term treatment, the subject may be permitted to remain in the study with permission from the Sponsor's Medical Monitor.
4. Use of benzodiazepines as rescue for innumerable seizure clusters more than three times in a 28-day period must be reviewed with Sponsor's Medical Monitor to assess suitability for continuation.
5. Subject's condition changes after entering the clinical investigation so that the subject no longer meets the inclusion criteria or develops any of the exclusion criteria;
6. Subject is noncompliant with procedures set forth in the protocol in an ongoing or repeated manner;
7. Subject experiences an adverse event (AE) that warrants withdrawal from the clinical investigation;
8. Patient's mean 28-day seizure rate over the past three 28-day periods before the study visit shows less than 35% improvement in comparison to the patient's baseline in the 1042-603 study;
9. It is the Investigator's opinion that it is not in the subject's best interest to continue in the study;

10. Any subject who exhibits any of the following will be immediately withdrawn from the clinical investigation:

- a. Clinically significant worsening of seizures as judged by Investigator or subject such that treatment outside of the protocol is assumed to be in the subject's best interest.
- b. Two episodes of generalized tonic-clonic seizures (GTCS) if not present in medical history.

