8.4.4 Selection of Doses in the Study

In meeting efficacy and tolerability criteria to participate in the study, it is expected that the subject will continue with the dose of ganaxolone (between 900-1800 mg/d) last prescribed in Study 1042-0603. Changes at V1 can be addressed with the Sponsor's Medical Monitor. During the study, the dose of ganaxolone may be adjusted at the Investigator's discretion based on tolerability and efficacy between 900 and 1800 mg/d, typically on the MTD of ganaxolone that provides adequate seizure control. Doses may be adjusted upward or downward in 225 mg/d increments every 3 days to reach an optimal dose level over the duration of the 52-week treatment period. Dose adjustments should be made with the investigator's agreement. Frequency of dosing changes may not be less than 3 days unless required for safety.

De-escalation Period: The study drug will be decreased in increments of 450mg/d in 4-day intervals over 12 days for 1800 mg. Decreases from doses less than 1800 mg will be adjusted accordingly (See [Table 2](#)). The subject will return for final post-taper safety assessment visit.

Details of the de-escalation regimen are provided in the table below.

Table 2. Dosing Schedule for De-Escalation Period

De-Escalation, Study Completion or Early Termination (ET)			
Visit	Taper Day	Dose (mg)/day	225 mg cap/day
Visit 7 (Study Completion/Early Term)	Last full dose	1800	8
	1	1350	6
	2	1350	6
	3	1350	6
	4	1350	6
	5	900	4
	6	900	4
	7	900	4
	8	900	4
	9	450	2
	10	450	2
	11	450	2
	12	450	2
	13	0	0
	14	0	0

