8.4.5 Dose Administration

Ganaxolone will be administered BID, 12 hours apart with food, i.e. 8:00 AM with breakfast and 8:00 PM after the evening meal. A missed dose of study medication may be taken later up to 8 hours before the next scheduled dose, otherwise the missed dose should not be given (See Section 8.4.6 Missing a Dose). It is important that ganaxolone be dosed with food.

The dose of ganaxolone may be adjusted based upon tolerability or efficacy. Subjects experiencing intolerable AEs at any dose level may have the dose reduced per Investigator direction to attempt to alleviate the event. See [section 8.4.4](#) for dosage adjustments and de-escalation procedures.

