1.1 STUDY OBJECTIVES

1.1.1 Primary Objective

To assess the safety and tolerability of adjunctive ganaxolone during two-year open label treatment in adult subjects with drug-resistant partial-onset seizures.

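### Tolerability is a primary objective under flexible dosing, but no planned SAP summary shows which adverse events led to a dose reduction

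*SAP*

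**What the plan says.** SAP 1.1.1 gives the primary objective: "To assess the safety and tolerability of adjunctive ganaxolone during two-year open label treatment in adult subjects with drug-resistant partial-onset seizures". Dosing is flexible. Under Protocol 8.4.4, "the dose of ganaxolone may be adjusted at the Investigator's discretion based on tolerability and efficacy between 900 and 1800 mg/d", and the same section expects subjects typically to be at their maximum tolerated dose.

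The protocol names two responses to a troublesome adverse event. Section 8.4.5 offers a lower dose: "Subjects experiencing intolerable AEs at any dose level may have the dose reduced per Investigator direction to attempt to alleviate the event". Section 8.3.4.1 offers withdrawal, item 7 being: "Subject experiences an adverse event (AE) that warrants withdrawal from the clinical investigation". Section 9.5.2 requires the response to be recorded: "Minimum information required for each AE includes type of event, duration (start and end dates), severity, seriousness, causality to study drug, action taken, and outcome". For analysis, Protocol 8.7.1.4 plans AE incidence both overall and by dose.

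The SAP 7.1 overview table counts subjects with TEAEs, serious AEs, drug-related TEAEs, TEAEs by severity, "TEAEs leading to study discontinuation", and TEAEs leading to death. SAP 7.1.1 adds listings of serious AEs, AEs leading to study discontinuation, and deaths. On dosing, SAP 5.1 says: "Exposure to study medication will be summarized as a continuous variable, via the number of days of drug taken". SAP Section 7 reports all safety results for a single ganaxolone group.

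**The concern.** When dose can be lowered for tolerability, the subjects who did not tolerate their dose fall into two groups: those who left and those who stayed on less drug. The overview identifies the first group and has no row for the second. Reductions are foreseeable, since subjects are expected to be near their tolerance limit.

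At stake is how the discontinuation row will be read. Subjects enter only after showing acceptable tolerability in Study 1042-0603 (Protocol 8.2), so few withdrawals for adverse events would not be surprising. Without a count of reductions, a reader cannot tell whether retention reflects tolerance of the dose or a move to a lower one.

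**Working it through.** The documents state no figure on this point and contain no sample-size or power calculation, so there is nothing to reproduce. The check has two parts.

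**1. Can any planned summary reveal a dose reduction?**

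| Planned output | Basis | Shows a reduction? |
|---|---|---|
| Overview: discontinuation row (SAP 7.1) | Subject left because of a TEAE | No, if the subject stayed |
| Severity tables (SAP 7.1) | Worst grade per preferred term | Event counted; link to dose lost |
| Relationship tables (SAP 7.1) | Closest relationship per preferred term | Event counted; link to dose lost |
| Exposure (SAP 5.1) | Stop date − start date + 1 | No dose term |
| Compliance (SAP 5.1) | Days taken as a share of days on drug | No dose term |
| Grouping of safety results (SAP 7) | One ganaxolone group | No dose strata |

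An interruption would lower compliance through the days not taken, but nothing would link it to an adverse event.

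The by-dose tabulation in Protocol 8.7.1.4 would have brought dose into the AE summaries. SAP Section 9 declares changes for ECG, neurological examination, C-SSRS, seizure-free measures, the global impression scales and endpoint naming. It does not mention AEs by dose.

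**2. The SAP 5.1 formulas applied to two assumed subjects**

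Inputs: planned treatment of 104 weeks (Protocol synopsis), so 104 × 7 = 728 days; starting dose 1800 mg/d, the top of the range. Subject A stays at 1800 mg/d. Subject B is reduced for an AE after t days. Neither misses a day, and both complete. The timing and depth of the reduction are my assumptions.

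- Exposure: 728 days for A and for B.
- Compliance: (728 − 0) / 728 × 100% = 100% for A and for B.
- Discontinuation row: no entry for A or for B.

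A mean daily dose, [1800t + L(728 − t)] / 728 with L the reduced dose, would separate them. A's mean is 1800 mg/d. B's is:

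| t (days) | L = 900 mg/d | L = 1350 mg/d |
|---|---|---|
| 28 | (50,400 + 630,000)/728 = 934.6 | (50,400 + 945,000)/728 = 1367.3 |
| 182 | (327,600 + 491,400)/728 = 1125 | (327,600 + 737,100)/728 = 1462.5 |
| 364 | (655,200 + 327,600)/728 = 1350 | (655,200 + 491,400)/728 = 1575 |

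Across these cases B receives between 51.9% (934.6/1800) and 87.5% (1575/1800) of A's dose, with identical exposure, compliance and discontinuation results. The study ended early, so 728 days is only the planned maximum. The identity does not depend on it: both formulas use days alone, so A and B agree for any shared duration.

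**The case against.** The strongest reply is that the event is not lost. It enters the incidence, severity and relationship tables, and the severity scale in Protocol 9.5.2 is itself based on functional impact. SAP 2.1 says the listings carry data collected on the eCRF, so action taken should be visible subject by subject. SAP Section 9 cites early termination and low numbers, and SAP 2.1 allows tables to be omitted when data are sparse, so reading reductions from a listing is defensible.

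Most of this stands, and it limits the point. A reader might infer that discontinuation is the SAP's only tolerability count, or that subjects who could not tolerate their dose vanish from the results. The documents do not support that: severity and relatedness also describe tolerability. What is missing is the link from event to dose change. Severity does not supply it, because the grade does not record whether the dose was cut.

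A reader might also add an assumed reduction rate to the discontinuation rate and call the sum the true figure. That is not supported either. The discontinuation row is correct as labelled, and no reduction rate is given. The 7.1% AE discontinuation rate quoted for Study 1042-0600 comes from a 10-week controlled study at 500 mg three times daily and cannot be carried over to this selected extension population.

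Nor did the protocol promise a dose-reduction table. Its subset listings cover AEs causing withdrawal and SAEs, and the SAP provides both. The undeclared departure is confined to AE incidence by dose.

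Finally, full dose summaries may not be feasible. The seizure calendar records only whether study drug was taken, and Protocol 8.4.10 describes quantities dispensed and returned, which mix reductions with missed capsules. No section shows an eCRF record of daily dose.

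**Conclusion.** The point holds as a gap in the planned summaries. Under the SAP as written, a subject who stayed only after a dose cut cannot be told apart, in any summary, from one with a similarly graded event who stayed on the same dose. A low discontinuation rate could therefore overstate tolerability across 900 to 1800 mg/d.

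The direction is clear, but the size is unknown: it depends on how many subjects were reduced for an AE and remained, which the documents do not report. If nobody was reduced, nothing changes except that the report can say so. The mean-dose figures show what one subject's record can hide; they do not estimate how often it happens.

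The conclusion assumes that action taken was recorded for each AE as Protocol 9.5.2 requires. The dropped by-dose tabulation is a separate matter of record and holds regardless. The change is worth making because it bears on the primary objective and its main element uses a required data item.

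**What to change.** 1. **SAP 7.1:** add an overview row, *TEAEs leading to dose reduction or interruption*, derived from the action-taken item, with a by-subject subset listing. If the data are too sparse for a table under SAP 2.1, provide the listing alone.
2. **SAP 5.1:** where dosing records allow, add each subject's entry and last daily dose and the number of subjects with a dose decrease. If the records do not allow it, say so.
3. **AE incidence by dose:** restore it, stating how an event is assigned to a dose, or declare and justify its removal in SAP Section 9.

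The overview row and listing need no new data. The dose summaries and the by-dose table depend on what the eCRF holds. The cost is a little more programming and a tolerability picture that may look less favourable.
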